5.8.2 Permitted therapy

Subjects are permitted to use topical, ocular, intra-articular, intranasal, and inhalational corticosteroids (with minimal systemic absorption). Adrenal replacement steroid doses of >10 mg daily prednisone are permitted. A brief (less than 3

weeks) course of corticosteroids for prophylaxis (e.g., contrast dye allergy) or for treatment of non-autoimmune conditions (e.g., delayed-type hypersensitivity reaction caused by a contact allergen) is permitted.

Steroid use should be minimized prior to inclusion. Systemic corticosteroid use or physiologic replacement doses of steroids are permitted, even >20 mg/day prednisolone equivalents, for: a) treatment-related AE or b) treatment of non-autoimmune conditions (e.g., prophylaxis for contrast dye allergy, contact hypersensitivity). Details regarding corticosteroid use prior to and during the study will be collected (name of medication, doses utilized, start and stop dates, frequency of use, route of administration). Information regarding concomitant corticosteroid use may be analyzed with regard to study outcome measures. Subjects requiring chronic treatment with corticosteroids should be treated with histamine-2 receptor antagonists or proton pump inhibitors as prophylaxis for potential gastrointestinal adverse reactions (ulceration, perforation, hemorrhage) unless otherwise contraindicated.

Support with granulocyte-colony stimulating factor (e.g., pegfilgrastim) in case of myelosuppression is permitted.

Oral anticoagulant therapy is permitted during study treatment breaks.

Concomitant medications are recorded at baseline and throughout the study treatment sequences. All medications (prescriptions or over-the-counter medications) continued at the start of the study or started during the study and different from the study drug will be documented.

All treatments that Clinical Investigator considers necessary for a subject's welfare may be administered at the discretion of Clinical Investigator in keeping with the community standards of medical care. All concomitant medication will be recorded, including all prescription, over-the-counter, and IV medications and fluids. If changes occur during the trial period, documentation of drug dosage, frequency, route, and date may also be recorded.

All concomitant medications received within 28 days before the first dose of study treatment and 30 days after the last dose of study treatment will be recorded. Concomitant medications administered later than 30 days after the last dose of study treatment should be recorded for SAE.

5.9 Subject numbering

Each subject is identified in the study by a unique subject number that is assigned when subject signs the ICF and is randomized. Once assigned the subject number cannot be reused for any other subject. The study treatment will be dispensed/administered to the subject by authorized site personnel only.

6 STUDY FLOW CHART

Trial period	Screening phase		Treatment sequence ¹							
Scheduling window; visit (V), cycle (C), day(D)	V-1 (D -15 to D-1)	V0 (D -14 to D0)	V1 C1 D1 (±3 days)	V2 C2 D1 (±3 days)	V3 C3 D1 (±3 days)	V4 C4 D1 (±3 days)	V5 C5 D1 (±3 days)	V6 C6 D1 (±3 days)	V7 C7 D1 (±3 days)	V8 C8 D1 (±3 days)
Administrative procedures										
Informed consent	X									
Inclusion/exclusion criteria		X								
Tumor (K)RAS/BRAF mutation status ³		X								
Medical history		X								
Prior ⁴ and concomitant medication review		X	X	X	X	X	X	X	X	X
Post-study anticancer therapy status										
Questionnaires (QoL)		X								
Clinical procedures										
Review adverse events		X	X	X	X	X	X	X	X	X
Full physical examination ⁷		X ⁸								
Directed physical examination			X	X	X	X	X	X	X	X
Vital signs and weight		X	X	X	X	X	X	X	X	X
ECOG performance status		X	X	X	X	X	X	X	X	X
Survival follow-up										
Laboratory procedures										
Pregnancy test ⁹		X ¹⁰			X ¹⁰		X		X ¹⁰	
HIV, HBV, and HCV tests		X								
Laboratory analyses ¹³		X	X	X	X	X	X	X	X	X
Urine analysis ¹⁵		X	X	X	X	X	X	X	X	X
Treatment administration										
FLOX			X	X	X ¹⁶	X ¹⁶	X	X	X ¹⁶	X ¹⁶
Nivolumab					X ¹⁶	X ¹⁶			X ¹⁶	X ¹⁶
Evaluation procedure(s)										
CT ¹⁷		X ¹⁸					X			
Correlative study procedures										
Whole blood sampling			X							
Plasma and serum sampling			X		X		X		X	
PBMC sampling ¹⁹			X		X		X		X	
Functional MR liver acquisition ^{19,20}		X			X		X			
Liver/peritoneal biopsy sampling ²¹		X			X		X			

Trial period	Break period ²	End of study visit	Withdrawal visit (if applicable)	Post-treatment phase		
Scheduling window; visit (V), cycle (C), day(D)	Every 8 weeks	At the time of treatment discontin.	At the time of withdrawal	Safety follow-up (approx. D30 after discontin.)	Follow-up year 1 after discontin. (every 3 months ±7 days)	Survival follow-up
Administrative procedures						
Informed consent						
Inclusion/exclusion criteria						
Tumor (K)RAS/BRAF mutation status ³						
Medical history						
Prior ⁴ and concomitant medication review	X	X	X	X		
Post-study anticancer therapy status				X	X	
Questionnaires (QoL)	X ⁵	X				
Clinical procedures						
Review adverse events	X	X	X ⁶	X ⁶	X ⁶	
Full physical examination ⁷				X		
Directed physical examination	X	X	X			
Vital signs and weight	X	X	X	X		
ECOG performance status	X	X	X	X		
Survival follow-up						X
Laboratory procedures						
Pregnancy test ⁹	X ¹¹	X	X	X	X ¹²	
HIV, HBV, and HCV tests						
Laboratory analyses ¹³	X	X ¹⁴	X ¹⁴	X ¹⁴	X ¹⁴	
Urine analysis ¹⁵	X	X ¹⁴	X ¹⁴	X ¹⁴	X ¹⁴	
Treatment administration						
FLOX						
Nivolumab						
Evaluation procedure(s)						
CT ¹⁷	X	X				
Correlative study procedures						
Whole blood sampling						
Plasma and serum sampling	X	X				
PBMC sampling ¹⁹	X	X				
Functional MR liver acquisition ^{19,20}						
Liver/peritoneal biopsy sampling ²¹						

- 1 Repeat after break period with disease progression, continue until progressive disease on ongoing therapy.
- 2 Until disease progression.
- 3 Analysis on primary or metastatic tumor.
- 4 Only at visit 2.
- 5 By completion of the active therapy of the first treatment sequence (after 16 weeks), *i.e.*, at first visit in first treatment break.
- 6 Until all study drug-related AE are resolved, have returned to baseline, or are deemed irreversible; reported for at least 100 days after last dose administration of IMP.
- 7 To be undertaken if clinically indicated from V1 onward, but mandatory at the 30 days safety follow-up visit.
- 8 May be omitted if full physical examination has been undertaken 14 days or less prior to the first dose of trial treatment.
- 9 For WOCBP.
- 10 Within 24 hours prior to the start of study drug.
- 11 Every 4 weeks.
- 12 Every 4 weeks; in the control arm, for 30 days after the last dose of study drug; in the experimental arm, for 160 days after the last dose of study drug.
- 13 Laboratory tests: Hb, HCT, WBC (including differential counting), platelets, liver factors (ALT, AST, ALP, LDH, GGT, total bilirubin, total albumin, INR), creatinine or urea, Na, K, Ca, Mg, phosphate, glucose, TSH, free T4, CEA, Ca19.9, Ca125.
- 14 Until all study drug-related abnormalities are resolved, have returned to baseline, or are deemed irreversible.
- 15 Dipstick.
- 16 FLOX in control treatment arm, nivolumab in experimental treatment arm.
- 17 In addition to computed tomography (CT) scan, MR scans or other radiologic evaluations will be performed if indicated.
- 18 Baseline CT scan must be taken within 28 days prior to the start of study drug.
- 19 Participation is optional for study centers.
- 20 Patient must not present contraindication to the procedure. Procedure must be done before a metastatic lesion in the liver/peritoneum is sampled.
- 21 Baseline sampling is mandatory; follow-up sampling is optional.

7 STUDY PROCEDURES

The Study Flow Chart (*Chapter 6*) summarizes study procedures to be performed at each visit. Individual procedures are described in detail below. It may be necessary to perform these procedures at unscheduled times if deemed clinically necessary by Clinical Investigator.

Furthermore, additional evaluation/testing may be deemed necessary by Sponsor and/or BMS for reasons related to subject safety. In some cases, such evaluation/testing may be potentially sensitive in nature (e.g., human immunodeficiency virus, hepatitis C), and thus local regulations may require that additional informed consent be obtained from the subject. In these cases, such evaluation/testing will be performed in accordance with those regulations.

7.1 Informed consent

Clinical Investigator will obtain documented consent from each subject prior to participation in the trial. Consent must be documented by the subject's dated signature on the ICF along with the dated signature of the person conducting the consent discussion. A copy of the signed and dated ICF will be given to the subject before participation in the trial.

The initial ICF, any subsequent revised written ICF, and any written information provided to the subject must receive approval of Institutional Review Board (IRB) and Independent Ethics Committee (IEC) in advance of use. The subject will be informed in a timely manner if new information becomes available that may be relevant to the subject's willingness to continue participation in the trial. The communication of this information will be provided and documented via a revised ICF or addendum to the original consent form that captures the subject's dated signature.

The informed consent will adhere to IRB/ERC requirements, applicable laws and regulations, and Sponsor requirements.

7.2 Inclusion and exclusion criteria

All inclusion and exclusion criteria will be reviewed by Clinical Investigator or a qualified designee to ensure that the subject qualifies for the trial.

7.3 Medical history

A medical history will be obtained by Clinical Investigator or a qualified designee. Medical history will include all active conditions, and any condition diagnosed within the prior 10 years that are considered to be clinically significant by Clinical Investigator. Details regarding the disease for which the subject has enrolled in this study will be recorded separately and not listed as medical history.

7.3.1 Prior medications

Clinical Investigator or a qualified designee will review prior medication use, including any protocol-specified washout requirement, and record prior medication taken by the subject within 28 days before starting the trial. Treatment for the disease for which the subject has enrolled in this study will be recorded separately and not listed as prior medication.

7.3.2 Concomitant medications

Clinical Investigator or a qualified designee will record medication, if any, taken by the subject during the trial.

7.3.3 Other diseases

Clinical Investigator or a qualified designee will obtain prior and current details regarding disease status.

7.3.4 Prior treatment details

Clinical Investigator or a qualified designee will review all prior cancer treatments including systemic treatments, radiation, and surgery.

7.3.5 Subsequent anti-cancer therapy status

Clinical Investigator or a qualified designee will review all new anti-neoplastic therapy initiated after the last dose of trial treatment. If a subject initiates a new anti-cancer therapy within 30 days after the last dose of trial treatment, the 30 day safety follow-up visit must occur before the first dose of the new therapy. Once new anti-cancer therapy has been initiated the subject will move into survival follow-up.

7.4 Safety assessments

At baseline, a medical history will be obtained to capture relevant underlying conditions. The baseline examinations will include weight, height, ECOG status, blood pressure, heart rate, and temperature, and will be performed within 14 days prior to first dose. Baseline signs and symptoms are those that are assessed within 14 days prior to first dose of study drug. Concomitant medications including steroid dose will be collected within 14 days prior to first dose of study drug and through the study treatment period.

Baseline local laboratory assessments will be done within 14 days prior to first dose and will include the following serum/plasma assessments: Hb, HCT, WBC (including differential counting), platelets, liver factors (ALT, AST, ALP, LDH, GGT, total bilirubin, total albumin, INR), creatinine or urea, Na, K, Ca, Mg, phosphate, glucose, TSH, free T4, CEA, Ca19.9, and Ca125. Additionally, urine analysis will be done.

The following baseline local laboratory assessments should be done within 28 days prior to first treatment: hepatitis B and C testing, according to each Institution's SOP.

Pregnancy testing of WOCBP must be performed within 24 hours prior to Day 1 and then every 4 weeks.

While on study treatment, the same local laboratory assessments as those of baseline will be done within 3 days prior to each dose.

Subjects will be evaluated for safety and tolerability if they have received any study drug. Toxicity assessments will be continuous during the treatment phase and formally recorded at each new therapy cycle, and every 8 weeks during planned breaks from active study therapy, and should be done in person. Once subjects reach the survival follow-up phase, either in-person or documented telephone calls to assess the subject's status are acceptable.

AE and laboratory values will be graded according to CTCAE v4.0.

The start and stop time of the study therapy infusions will be documented.

Additional measures, including non-study required laboratory tests, will be performed as clinically indicated or to comply with local regulations. Laboratory toxicities (*e.g.*, suspected drug-induced liver enzyme evaluations) will be monitored during the follow-up phase via local laboratories until all study drug-related toxicities resolve, return to baseline, or are deemed irreversible.

Some of the assessments referred to in this section may not be captured as data in the CRF. They are intended to be used as safety monitoring by the treating physician. Additional testing or assessments may be performed as clinically necessary or where required by institutional or local regulations.

7.5 Physical examination

7.5.1 Full physical examination

Clinical Investigator or a qualified designee will perform a complete physical examination during the screening period. Clinically significant abnormal findings should be recorded as medical history. A full physical examination will also be performed at the 30 days safety follow-up visit and if clinically indicated otherwise during the study.

7.5.2 Directed physical examination

For study visits that do not require a full physical examination as per Study Flow Chart, Clinical Investigator or a qualified designee will perform a directed physical examination as clinically indicated prior to trial treatment administration.

7.5.3 Vital signs

Clinical Investigator or a qualified designee will take vital signs at screening, prior to the administration of each dose of trial treatment, and at treatment discontinuation as specified in Study Flow Chart. Vital signs should include temperature, pulse, weight, and blood pressure. Height will be measured at screening only.

7.5.4 ECOG performance status

Clinical Investigator or a qualified designee will assess ECOG status at screening, prior to the administration of each dose of trial treatment, every 8 weeks during planned breaks from active study therapy, at discontinuation of trial treatment, and during follow-up, as specified in Study Flow Chart.

7.6 Tumor imaging and assessment of disease procedures

7.6.1 Evaluation of efficacy

The imaging assessments will be performed by CT, typically a thoracic/abdominal/pelvic CT scan. Tumor treatment response will be assessed according to RECIST v1.1 as the primary method and iRECIST as the secondary method. After baseline tumor assessments, evaluation of tumor response will be performed every 8 weeks (± 7 days). Additional MR scans or other radiologic evaluations will be performed if indicated.

All radiologic examinations will be transmitted to Study Radiologist at Akershus University Hospital within 1 working day after the scan is performed. A radiologist at the actual study center will evaluate the images for incidental findings that may have a therapeutic consequence (e.g., pulmonary embolism, immune therapy-related findings that require emergency actions).

Study Radiologist will be blinded to patient treatment, but will be informed about treatment breaks in the go-and-stop schedule. Study Radiologist will primarily assess tumor measures according to RECIST v1.1. If disease progression is concluded by means of RECIST v1.1, Study Radiologist will also assess tumor measures according to iRECIST. The radiology report will detail the criteria used for Clinical Investigator to make a decision about further study treatment (*c.f.*, [Paragraph 5.7.2.4](#)).

PFS will be calculated from the day of randomization to first recorded disease progression according to RECIST v1.1 or iRECIST when applicable, or death. Patients who have not had disease progression at the time of final analysis will be censored at the date last known to be alive and progression-free.

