CR	PD	SD provided minimum criteria for SD duration met, otherwise, PD	
CR	NE	SD provided minimum criteria for SD duration met, otherwise NE	
PR	CR	PR	
PR	PR	PR	
PR	SD	SD	
PR	PD	SD provided minimum criteria for SD duration met, otherwise, PD	
PR	NE	SD provided minimum criteria for SD duration met, otherwise NE	
NE	NE	NE	

* may consider PR providing initial "CR" likely PR on subsequent review – then original CR should be corrected. Recurrence of lesion after true CR is PD.

7.6.4 iRECIST

In the experimental arm, iRECIST will be used in the case of new lesion(s) or increase in size of known lesion(s), and if the patient is clinically deteriorating. This is categorized as *immune-unconfirmed progressive disease* (iUPD). An *immune-confirmed progressive disease* (iCPD) is only assigned if at next assessment after iUPD (4–8 weeks later) additional new lesions appear or an increase in size of new lesions is seen (≥ 5 mm for sum of new target lesion or any increase in new non-target lesion). The appearance of new lesions when none have previously been recorded can also confirm iCPD.

However, if progression is not confirmed but instead tumor shrinkage occurs (compared with baseline), which meets the criteria of *immune-complete response* (iCR), *immune-partial response* (iPR), or *immune-stable disease* (iSD), then the bar is reset so that iUPD needs to occur again (compared with nadir values) and then be confirmed (by further growth) at the next assessment, for iCPD to be assigned. If no change in tumor size or extent from iUPD occurs, then the time point response would again be iUPD. This approach allows atypical responses, such as delayed responses that occur after pseudoprogression, to be identified, further understood, and better characterized.

Response criteria are essentially based on a set of measurable lesions identified at baseline as target lesions, and, together with other lesions that are denoted as non-target lesions, followed until disease progression.

For direct comparison of iRECIST with RECIST v1.1 [Seymour *et al.*, 2017], please refer to **Appendix 2**.

iCR or iPR may be claimed only if the criteria for each are met at a subsequent time point at least 8 weeks later.

Assignments of timepoint response using iRECIST:

	Timepoint response with no previous iUPD in any category	Timepoint response with previous iUPD in any category
Target lesions: iCR; non-target lesions: iCR; new lesions: no	iCR	iCR

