7.10.4 Repeat functional MR imaging

Experimental arm patients will undergo repeat MR recordings of abdominal metastases at time points corresponding to each change of therapy (from FLOX to nivolumab and reverse) during the first two months of the sequential regimen (*i.e.*, three recordings in total), using a discrete number of functional MR sequences with readouts reflecting TME biology. Specifically, we will apply our recently developed multi-echo contrast-enhanced sequence, which can predict metastatic progression with high diagnostic accuracy [Grøvik *et al.*, 2016]. Importantly, the MR procedure must be done before a metastatic lesion is sampled by biopsy. Control arm patients may be exempt from MR imaging at the discretion of Clinical Investigator. Please refer to the specified SOP document (in Investigator Site File).

Participation in the functional MR imaging biomarker sub-study is optional for study centers.

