10.2.2 Blinding

Study Statistician (along with Study Radiologist) will not have access to the information on treatment arms before the study conduct is concluded and all analyses have been performed. An emergency unblinding for Study Statistician should not be required at any time of the study conduct since EDSMC will oversee the trial during its entire course (*c.f.*, [Paragraph 9.4](#)).

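### The Study Radiologist's blinding is not protected: sub-study functional MRs are not excluded from what this reader receives, and the iRECIST rule in 7.6.4 needs arm and clinical status

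*Protocol*

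**What the plan says.** Blinding is promised in two places. Protocol 7.6.1: "Study Radiologist will be blinded to patient treatment, but will be informed about treatment breaks in the go-and-stop schedule". Protocol 10.2.2: "Study Statistician (along with Study Radiologist) will not have access to the information on treatment arms before the study conduct is concluded".

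On what the reader receives, 7.6.1 states: "All radiologic examinations will be transmitted to Study Radiologist at Akershus University Hospital within 1 working day after the scan is performed". It names no exception.

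On functional MR, 7.10.4 states: "Experimental arm patients will undergo repeat MR recordings of abdominal metastases at time points corresponding to each change of therapy". The schedule is three recordings within the first two months, counting baseline. The same paragraph adds: "Control arm patients may be exempt from MR imaging at the discretion of Clinical Investigator". Centers may choose whether to take part (7.10.4; flow chart footnote 19), and patients with a contraindication are excluded (footnote 20). The flow chart places the recordings at V0, V3 and V5.

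On iRECIST, 7.6.1 has the Study Radiologist add an iRECIST assessment whenever RECIST v1.1 shows progression, with no arm mentioned. Section 7.6.4 reads differently: "In the experimental arm, iRECIST will be used in the case of new lesion(s) or increase in size of known lesion(s", and it adds clinical deterioration as a condition. Section 7.6.6 dates progression by RECIST PD in the control arm and by iCPD in the experimental arm. The SAP uses both criteria for PFS (5.1, 5.2) but does not mention the Study Radiologist.

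**The concern.** The trial is open-label and its primary end point depends on reading scans. The blinded central read is the main protection of PFS against assessment bias, and its report also reaches the investigator while treatment is under way (7.6.1, 5.7.2.4). Calls near the 20% growth threshold, a possible new lesion, or unequivocal non-target progression leave room for judgement. A reader who can guess the arm may lean on such calls without meaning to.

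Two features of the text work against the blinding. A type of examination expected more often in one arm appears to be sent to the reader. And one version of the reading rule can be followed only by someone who knows the arm and the patient's clinical condition.

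**Working it through.** The plan gives no figure to reproduce here. The check is textual, with a short calculation of how informative the cue could be.

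**1. Timing.** Cycles are every 2 weeks (5.4), so V3 (cycle 3, day 1) is day 1 + 2 × 14 = day 29, after 4 weeks. V5 (cycle 5, day 1) is day 1 + 4 × 14 = day 57, after 8 weeks. In the flow chart the first on-treatment CT is at V5 and no CT is scheduled at V3. The week-4 MR therefore comes before the first response read and stands alone. The week-8 MR falls at the same visit as that CT.

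**2. Strength of the cue at a participating center.** Let *e* and *c* be the shares of experimental and control patients who have a post-baseline functional MR. With 1:1 allocation (10.2.1):

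P(experimental | MR seen) = *e* / (*e* + *c*)

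The documents give neither *e* nor *c*, so these are assumed ranges:

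| *e* | *c* | P(experimental given MR) |
|---|---|---|
| 1.0 | 0 | 1/1 = 100% |
| 1.0 | 0.5 | 1/1.5 = 67% |
| 1.0 | 1.0 | 1/2 = 50% (no information) |
| 0.8 | 0 | 0.8/0.8 = 100% |
| 0.8 | 0.2 | 0.8/1.0 = 80% |
| 0.8 | 0.5 | 0.8/1.3 = 62% |

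**3. Reach across the trial.** Let *s* be the share of patients at participating centers, also not given. The best-guess accuracy at those centers is A = ½·max(*e*, *c*) + ½·max(1−*e*, 1−*c*). Over the whole trial it is *s*·A + (1−*s*)·½.

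- *e* = 1, *c* = 0: A = 0.5 + 0.5 = 1. Overall accuracy is 50%, 62.5%, 75% and 100% for *s* = 0, 0.25, 0.5 and 1.
- *e* = 1, *c* = 0.5: A = 0.5 + 0.25 = 0.75. Overall accuracy is 50%, 56%, 62.5% and 75% for the same *s*.

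**4. The iRECIST rule.** Set side by side:

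- 7.6.1: iRECIST after any RECIST progression, by the blinded reader, arm not stated.
- 7.6.4: iRECIST in the experimental arm, with clinical deterioration as a condition.
- 7.6.6: the progression date uses a different criterion in each arm.
- 10.2.2: neither the Study Radiologist nor the Study Statistician knows the arm until the end.
- Appendix 2: clinical stability bears on whether treatment continues after iUPD, not on the scan reading.

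A blinded reader can follow 7.6.1 but not 7.6.4. No section names the person who applies 7.6.6.

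**The case against.** The strongest reply is that the transmission sentence was never meant to cover functional MR. It stands in a section on efficacy imaging, defined there as CT, with the addition that "Additional MR scans or other radiologic evaluations will be performed if indicated". Functional MR is not mentioned in 7.6. The flow chart lists it among correlative procedures, apart from CT. Section 7.10.4 refers to an SOP that is not among the documents and that may set who receives these scans. This stands as a plausible reading, but it is not written in the protocol or SAP, and the literal text says otherwise.

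Second, a reader might infer that the Study Radiologist learns the arm of every experimental patient. The documents do not support that. The sub-study is optional for centers and belongs to a list that 7.10 calls non-mandatory. Control exemption is allowed, not imposed, and the flow chart marks the MRs without separating the arms. Only the week-4 MR clearly precedes the first read.

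Third, one could try to put a size on the bias. Fifty experimental patients × 2 post-baseline MRs gives 100 examinations, but only if every center joins and every patient is scanned. Moving 10–25% of progression calls by one 8-week visit gives 0.8–2 weeks of mean PFS, but that share has no source in the documents, and the planned analysis is a log-rank test and a Cox hazard ratio.

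Fourth, 7.6.4 does not name the Study Radiologist, and unblinded staff could apply the arm-specific rule after the read. That would work, but no section assigns it to them. It would also be wrong to call the central read the only blinded element, since 10.2.2 blinds the statistician too.

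**Conclusion.** The concern holds in a limited form. Read literally, the protocol gives the blinded PFS reader a probabilistic cue to the arm at centers in the functional MR sub-study, as early as week 4, and neither the protocol nor the SAP contains a safeguard. The cue ranges from no information (all controls scanned) to near certainty (none scanned). This rests on the transmission sentence including functional MR and on uptake that the documents do not report. The size of any PFS bias cannot be stated, and the documents do not show that blinded assessment has failed.

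The conflict between 7.6.1 and 7.6.4 does not depend on MR uptake. It is a contradiction in the reader's instructions and, together with 7.6.6, has to be reconciled. Both matters merit a wording change because the remedy is cheap and the primary end point depends on this read.

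**What to change.** 1. In 7.6.1, limit what is sent to the Study Radiologist to CT and any other imaging used for RECIST/iRECIST. Keep functional MR in the sub-study archive, unopened by this radiologist until that patient's response reads are locked. The local radiologist already checks images for incidental findings (7.6.1). Cost: later functional MR reads if this radiologist is to make them.

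2. State that the blinded reader reports RECIST v1.1 and, after any RECIST progression in either arm, iRECIST, without knowing arm or clinical status. Cost: a few additional iRECIST reads in control patients.

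3. Reconcile 7.6.4 and 7.6.6 with this, and name who applies any arm-specific dating of progression or any use of clinical status, so that both happen outside the blinded read. How those rules bear on continuing treatment is for the sponsor to settle when the sections are aligned.

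These are changes to routing and wording. No extra scan or reader is needed.
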